Pressurised metred dose inhaler (pMDI) and Diskus devices both deliver fluticasone/salmeterol combination therapy, but the Diskus formulation includes added lactose. A previous Research in Real Life study [4] demonstrated that asthma patients on combination therapy via pMDI have significantly greater odds of achieving asthma control and fewer exacerbations than those on dry powder inhalers such as Diskus.

This study aims to explore and identify the benefits of using either pMDI versus Diskus for delivering fluticasone/salmeterol combination therapy in patients with COPD.

This study will focus on patients with COPD initiating with Seretide[®] combination therapy, delivered via

- pMDI (also known as Evohaler)
- Diskus (also known as Accuhaler)

In addition, the number of patients in the following sub-populations will be reported:

ⁱ COPD is defined as a common, preventable and treatable disease characterised by persistent airflow limitation that is usually progressive and associated with an enhanced chronic inflammatory response in the airways and lungs to noxious particles and gases.

ⁱⁱ Therapeutic index = highest dose not causing harm (side effect) / lowest dose that causes benefit (reduced number of severe COPD-related events).

- COPD without asthma
- COPD with asthma
- COPD +/- asthma AND eosinophils $>0.4 \times 10^9/L$

DATASOURCE

This study will use the Optimum Patient Care Research Database (OPCRD), which comprises anonymous data extracted from primary care practices in order to perform reviews of their chronic respiratory services. Two types of anonymised patient data are typically collected:

- (1) Routine clinical data
 - OPC software interfaces with primary care practice management systems and extracts disease coding and prescribing information.
- (2) Questionnaires
 - Patients identified as recipients of the respiratory service under review are invited to complete validated disease assessment questionnaires to better understand their current health status (and/or possible reasons for sub-optimal status).
 - Anonymised questionnaires are assigned a unique code to aid matching routine data to questionnaire results.

The OPCRD has been approved by Trent Multi Centre Research Ethics Committee for clinical research use. The anonymous, longitudinal patient data offers a high-quality data source for use in clinical, epidemiological and pharmaceutical research. It enables research to be carried out across a broad range of respiratory areas.

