STUDY DESIGN

The study will be a retrospective database analysis, consisting of a (one year) baseline period, a (one year) outcome period and an index date, defined as the date of the first prescription for Seretide[®] combination therapy at which patients with evidence of COPDⁱⁱⁱ will be split into the following groups:

- (1) Those using pMDI (also known as Evohaler)
- (2) Those using Diskus (also known as Accuhaler)

The baseline period will be one year prior to and including the index date^{iv} and it will be used for patient characterisation, such as demographics, baseline therapy, disease severity and number of COPD exacerbations. The outcome period will be one year following the index date, and the effect of device on COPD-related severe exacerbations, adverse events and therapeutic index will be investigated.

ⁱⁱⁱ COPD diagnostic code (at any time) and recorded spirometry data supporting COPD diagnosis within 5 years window of diagnosis code. Note that individuals with asthma and bronchiectasis will not be excluded.

^{iv} except for therapy prescribed at IPD (which is included in the outcome).

[figure not shown]

Figure 1: Study design

Inclusion Criteria

In order to be included in the study, patients must fit the following criteria:

- (1) COPD diagnosis (COPD diagnostic code (at any time) and COPD confirmed by FEV/FVC ratio <0.7 ever in medical history. Note that individuals with asthma and bronchiectasis will not be excluded)
- (2) Two years of continuous practice data comprising 1 year baseline data and 1 year outcome data
- (3) ≥2 prescriptions for Seretide® pMDI OR Seretide® Diskus during 1 year outcome period, inclusive of IPD (i.e. 1 Seretide® prescription at IPD plus ≥1 prescriptions for the same device during 1 year outcome period).
- (4) Age ≥35 at time of initiating with Seretide

Exclusion Criteria

- (1) Evidence of restrictive lung disease other than bronchiectasis (diagnostic code)
- (2) ≥1 prescription for inhaled corticosteroids (ICS), including as part of a fixed dose combination, during baseline period (excluding IPD)
- (3) Evidence of pneumonia during baseline period (diagnostic code)
- (4) No maintenance oral steroids in baseline

Dataset Variables

Demographics (gender, age, weight, height, BMI, smoking status, disease severity (FEV1 percent predicted, FEV1/FVC ratio, GOLD group, mMRC score)) will be calculated at (or closest to) the IPD. Disease severity will be regarded as missing if >5 years either side of IPD.

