Treatment therapy will be recorded in the year prior to the IPD.

Baseline blood eosinophil counts will be recorded^v (where valid is defined as a numeric value expressed /L).

Co-morbidities will be examined regardless of when diagnosis relative to the index date was made and include:

- Ischaemic heart disease
- Heart failure diagnosis
- Diabetes diagnosis
- Asthma diagnosis
- Bronchiectasis diagnosis
- Rhinitis
- Eczema
- Osteoporosis diagnosis
- Gastroesophageal reflux disease (GERD)
- Anxiety/depression diagnosis
- Chronic kidney disease
- Hypertension

Note that all of the above co-morbidities (except diabetes) are identified by GP diagnostic read code, ever recorded. Diabetes is identified by GP anti-diabetic drug prescriptions; AND/OR by GP diagnostic read code, ever recorded.

For the baseline and outcome periods, the following will be calculated:

- COPD exacerbations^{vi} and the date of event (each component of the definition will also be analysed separately)

^v closest value to IPD (missing if >5 years either side of IPD).

^{vi} Where an exacerbation is defined as an occurrence* of:

- COPD-related: Unscheduled hospital admission / A&E attendance^{**}; OR
- An acute course of oral steroids prescribed with evidence of a respiratory review^{***}; OR
- Antibiotics prescribed with evidence of a respiratory review^{***}.

*Where ≥ 1 oral steroid course / hospitalisation / antibiotics prescription occur within 2 weeks of each other, these events will be considered to be the result of the same exacerbation (and will only be counted once).

****COPD-related Hospitalisations:** consist of either a definite COPD Emergency Attendance or a definite COPD Hospital Admission; OR a generic hospitalisation read code which has been recorded on the same day as a **Lower Respiratory Consultation**[§] (see below - excluding where the only lower respiratory code recorded on that day was for a lung function test).

*****Evidence of a Respiratory Review** - consists of the following:

- a) Any **Lower Respiratory Consultation**[§] (see below) and
- b) Any additional respiratory examinations, referrals, chest x-rays, or events.

§ Lower Respiratory Consultations - consist of the following:

- a) Lower Respiratory read codes (including Asthma, COPD and LRTI read codes);

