- Development of pneumonia (recorded as absence/presence of, and confirmed via: chest X-ray within a month of a pneumonia diagnosis OR hospitalisation within a month of a pneumonia diagnosis). Note that baseline values will be zero due to study exclusion criteria.
- Development/progression of diabetes
 - Development of diabetes (recorded as absence or presence of) during outcome period for patients (for patients without diabetes at or prior to IPD)
 - Progression of ongoing type-II diabetes treatment to insulin (defined as no insulin prescription during 1 year baseline period AND any insulin prescriptions during 1 year outcome period)
 - Diabetic control (defined as change in HbA1c value prior to starting Seretide® and after IPD)
 - Diabetic medication (defined as change in anti-type-II diabetic medication dosage OR medication type)
- Number of potential severe COPD-related adverse events and date of event including
 - Oral thrush
 - Lower respiratory tract infections
 - Bronchitis
 - Dysphonia / hoarseness
 - Nasopharyngitis (common cold)
 - Sinusitis
 - Hypokalemia (low blood potassium)
 - Muscle or joint pain
- ICS dose (in outcome period only) and date of ICS prescription

Matching will be used if required.

STUDY OUTCOMES

The primary aim of the current study is to identify baseline and outcome characteristics of patients with COPD initiating with Seretide® combination therapy via pMDI and Diskus and to identify and compare the potential benefits of using each device in the delivery of Seretide®. Among other events, the effect of device on the following outcomes will be investigated:

(1) COPD related severe exacerbations

Where an exacerbation is defined as an occurrence^{vii} of:

- COPD-related: Unscheduled hospital admission / A&E attendance^{viii}; OR
- An acute course of oral steroids prescribed with evidence of a respiratory review^{ix};
OR

-
- b) Asthma/COPD review codes excl. any monitoring letter codes;
 - c) Lung function and/or asthma monitoring.

^{vii}Where ≥ 1 oral steroid course / hospitalisation / antibiotics prescription occur within 2 weeks of each other, these events will be considered to be the result of the same exacerbation (and will only be counted once).

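### Exclusion criterion (4) is worded the wrong way round: read literally, it removes patients without maintenance oral steroids and keeps only those on them

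*Protocol*

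**What the plan says.** In the protocol's Study Design section, the list headed Exclusion Criteria has four items. The first three are:

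- Item 1: "1) Evidence of restrictive lung disease other than bronchiectasis (diagnostic code".
- Item 2: "≥1 prescription for inhaled corticosteroids (ICS), including as part of a fixed dose combination, during baseline period (excluding IPD".
- Item 3: "3) Evidence of pneumonia during baseline period (diagnostic code".

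The fourth is "4) No maintenance oral steroids in baseline".

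The separate inclusion list opens with "In order to be included in the study, patients must fit the following criteria". The Background describes the population in general terms: "This study will focus on patients with COPD initiating with Seretide" combination therapy by either device. The Objectives and the Study Outcomes section describe it in the same way. Maintenance oral steroids appear nowhere else in the text. Oral steroids otherwise appear only in the exacerbation definition, where one component is "An acute course of oral steroids prescribed with evidence of a respiratory review" (Dataset Variables, footnote vi, repeated under Study Outcomes).

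**The concern.** An item in an exclusion list states what removes a patient. Item 4 states something a patient would have to satisfy in order to enter, so its wording and its heading point in opposite directions.

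The study is a retrospective database analysis. The eligibility lists are therefore rules to be applied to records, and the protocol describes no patient-by-patient judgement at enrolment that would catch a reversed rule. Code that follows the text selects the opposite group on this criterion. Code that follows the presumed intent departs from the written protocol, and nothing records that it did.

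**Working it through.** The protocol gives no figure on this point to reproduce, so the check is one of logic and consistency.

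**Step 1: how the protocol uses its exclusion list.** Items 1 to 3 name restrictive lung disease, a baseline inhaled steroid prescription and baseline pneumonia. In each, the presence of the feature removes the patient. The Dataset Variables section applies the list in that sense. Of pneumonia it says "Note that baseline values will be zero due to study exclusion criteria", which is true only if patients who meet a listed condition are taken out.

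**Step 2: apply the same convention to item 4.** Let M mean that the patient is on maintenance oral steroids in the baseline period. The listed condition is not-M.

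| Patient | Listed condition (not-M) | Item 4 as written | Item 4 without *No*, or moved to the inclusion list |
|---|---|---|---|
| On maintenance oral steroids (M true) | false | retained | removed |
| Not on them (M false) | true | removed | retained |

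The last two columns are complements. On this criterion no patient is eligible under both readings.

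**Step 3: compare with the stated population.** The Objectives, Background and Study Outcomes sections describe COPD patients starting Seretide by one device or the other. The sub-populations to be counted are defined by asthma status and eosinophil count. None of this restricts the study to users of maintenance oral steroids, so the literal reading of item 4 conflicts with every description of the population.

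**Step 4: look for a correcting statement.** There is none in the text, because the term occurs only in item 4.

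**Step 5: size.** Let p be the share of otherwise eligible patients with M true. The literal rule keeps p and the other reading keeps 1 − p. The protocol gives no value for p. Purely as an illustration, if p were assumed to lie between 1% and 5%, the literal rule would keep 1% to 5% and drop 100% − 5% = 95% to 100% − 1% = 99%. That range only restates the assumption and is not an estimate.

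**The case against.** The strongest reply is that the meaning is not in real doubt. Item 2 removes prior inhaled steroid users and item 3 removes patients with baseline pneumonia. Removing maintenance oral steroid users fits that pattern, whereas keeping only such users does not. A stray *No* in an exclusion list is a common slip, and a careful programmer would probably read through it. That stands: the intended direction can be inferred, and this is better described as an inconsistency between an item and its heading than as a deliberate design choice. It does not make the line correct. A rule that decides who is in the study should not need its reader to override it.

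A reader might go further and infer that the literal rule would yield a small, very severe, steroid-dependent cohort, that oral steroid effects would drown any device difference, and that the study could not answer its question. The protocol does not support these steps:

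- It says nothing about how common maintenance use is or how ill such patients are.
- Its Background links inhaled, not oral, corticosteroids to pneumonia, diabetes and thrush.
- An exposure shared by every patient in both device groups would raise background risk and narrow generalisability. It would not in itself hide a between-device difference.

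A reader might also argue that acute courses could not be told apart from maintenance prescribing under the literal rule. The difficulty is plausible, but the protocol does not establish it. The definition already specifies an acute course with evidence of a respiratory review, this is one of three exacerbation components, and each component is also analysed separately.

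The protocol does not define maintenance use. A statistical analysis plan that is not at hand may do so, and that gap is not part of this point.

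**Conclusion.** Wrong as written. Item 4 runs opposite to its heading, to the other three items and to the population the protocol describes, and nothing in the text corrects it. It is most likely a drafting slip. It needs correction because eligibility text must be unambiguous and the two readings give non-overlapping cohorts, not because the study can be shown to fail.

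The number of patients affected is unknown. Any harm arises only if the literal wording is what gets programmed, and the protocol does not say how the extraction code is derived. The conclusion rests on the text alone; Figure 1 was not available to check.

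**What to change.** Reconcile item 4 with its heading and with the stated population in one of two ways:

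- Delete *No*, so that the item names maintenance oral steroid therapy during the baseline period as a reason for exclusion.
- Leave the wording as it is and move the line to the inclusion list.

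Both give the same cohort. Then confirm that the extraction code applies the criterion in that direction. The cost is one line of protocol text and one check of the code.

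### Characterisation variables may be taken from after the index date, so post-treatment information, including incident diabetes, can enter the by-device description and any matching based on it

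*Protocol*

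**What the plan says.** The Study Design section fixes the baseline window: "The baseline period will be one year prior to and including the index date". It also states the purpose: "it will be used for patient characterisation, such as demographics, baseline therapy, disease severity and number of COPD exacerbations".

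The Dataset Variables section then sets different windows:

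- **Co-morbidities:** "Co-morbidities will be examined regardless of when diagnosis relative to the index date was made and include". The note under the list repeats this for all conditions but one: "all of the above co-morbidities (except diabetes) are identified by GP diagnostic read code, ever recorded". For the remaining one: "Diabetes is identified by GP anti-diabetic drug prescriptions; AND/OR by GP diagnostic read code, ever recorded".
- **Severity** (FEV1 % predicted, FEV1/FVC, GOLD group, mMRC): the value at or closest to IPD, with the limit "Disease severity will be regarded as missing if >5 years either side of IPD".
- **Blood eosinophils**, which the text itself calls baseline counts: "closest value to IPD (missing if >5 years either side of IPD" (footnote v).

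Diabetes also appears as an objective of the device comparison, and under Dataset Variables as an outcome: "Development of diabetes (recorded as absence or presence of) during outcome period for patients (for patients without diabetes at or prior to IPD".

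By contrast, baseline therapy is limited to the year before IPD.

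**The concern.** A variable that describes the arms at treatment start should not depend on what happened afterwards. Under these definitions it can. Heart failure, osteoporosis or asthma first coded after initiation counts the same as a long-standing diagnosis. A lung function, mMRC or eosinophil value may be taken after months or years of treatment, exacerbations and oral steroid courses.

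Diabetes is the clearest case, because one event is both an outcome of the device comparison and a characteristic used to describe the arms.

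Characterising the arms is the first objective and part of the primary aim. The same variables supply the asthma and eosinophil sub-populations in the Background section. They are also the likely basis for deciding whether matching, which the protocol allows if required, is needed.

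**Working it through.** The protocol gives no sample size, event rate or prevalence, so there is no figure to reproduce. The check has two parts.

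**1. The windows side by side**

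| Item | Window | Can it fall after IPD? |
|---|---|---|
| Baseline period (Study Design) | 1 year up to and including IPD | No |
| Baseline therapy | Year before IPD | No |
| Severity | Closest value, up to 5 years either side | Yes, up to 5 − 1 = 4 years past the outcome year |
| Eosinophils | Closest value, up to 5 years either side | Yes, same bound |
| Co-morbidities, including asthma and diabetes | Ever recorded | Yes, no bound |
| Diabetes outcome | Outcome year, in patients free of diabetes at or before IPD | Correctly after IPD |

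The variable windows contradict the baseline definition. A patient with a first diabetes code or anti-diabetic prescription in the outcome year meets the outcome and, by the ever-recorded rule, the co-morbidity too.

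**2. Illustration for diabetes (all rates assumed)**

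Let p be prevalence at IPD, equal in both arms, and i the one-year incidence among those at risk.

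- Ever-diabetes share: e = p + (1 − p) × i
- Share of the ever group that is new: s = (1 − p) × i / e
- After 1:1 matching on ever-diabetes, with common share e, risk of new diabetes among those free of it at IPD: r = e × s / [(1 − e) + e × s]

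With p = 10% and i = 1% v 2%:

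- e = 0.10 + 0.90 × 0.01 = 0.109, v 0.10 + 0.90 × 0.02 = 0.118. Arms with equal prevalence look like 10.9% v 11.8%.
- s = 0.009 / 0.109 = 8.3%, v 0.018 / 0.118 = 15.3%.
- Matched at e = 0.109: r = 0.009 / (0.891 + 0.009) = 0.0100, v 0.01663 / (0.891 + 0.01663) = 0.01832.
- Risk ratio = 0.01832 / 0.0100 = 1.83, against a true 2.00.

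The same formulas over the assumed range give:

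| Incidence | True ratio | p = 5% | p = 10% | p = 15% |
|---|---|---|---|---|
| 1% v 1% | 1.00 | 1.00 | 1.00 | 1.00 |
| 1% v 1.5% | 1.50 | 1.38 | 1.43 | 1.45 |
| 1% v 2% | 2.00 | 1.71 | 1.83 | 1.88 |
| 2% v 4% | 2.00 | 1.55 | 1.71 | 1.79 |

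With diabetes status cut off at IPD, the covariate equals p in both arms, and matching on it leaves 2.00 at 2.00 and 1.50 at 1.50. Codes first recorded after the outcome year would add to the contamination and are not modelled.

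The first row depends on equal prevalence. With p = 10% v 15% and incidence 1% in both arms, s = 0.009 / 0.109 = 8.26% v 0.0085 / 0.1585 = 5.36%. Matched at e = 0.109, r = 0.0100 v 0.00585 / (0.891 + 0.00585) = 0.0065, a ratio of 0.65 with no true effect.

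**The case against.** The strongest reply is that little of this reaches the device effect as the protocol stands. Much of that is right:

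- **The diabetes outcome is sound.** It is limited to patients without diabetes at or before IPD. The overlap runs from the outcome into the covariate, not the other way.
- **Only unadjusted tests are named.** The Statistical Analysis section lists t-test, Mann-Whitney and chi-square comparisons, none of which uses these covariates. Matching is conditional and its variables are not named. A reader might infer that the device effect will be biased, or that its odds ratio becomes uninterpretable. The document does not support that without such use.
- **The closest-value rule limits late values.** A post-index measurement enters only when it is nearer to IPD than any earlier one, and 5 years is the outer bound. A reader might suppose that about half the values are post-treatment. That needs measurement times symmetric around IPD, for which the protocol offers nothing.
- **The co-morbidity rule is open about its timing** and does not use the word baseline. It is therefore too strong to say that all incident cases are misclassified. They are classified as defined; the fault is the overlap with an outcome and with the stated purpose of the baseline period.
- **The sub-populations are only counted.** No device comparison within them is specified.

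A two-sided window also buys completeness, which is a legitimate aim in routine data.

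What this does not answer is the contradiction itself. The windows are written rules, not details left for a later plan. Followed as written, they mix pre- and post-treatment information in tables that serve the first objective. The study's exploratory label does not remove that.

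**Conclusion.** The point holds, with limited reach. The definitions of co-morbidities, severity and eosinophils conflict with the protocol's own baseline period.

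Three consequences follow from the text alone: a by-device characteristics table that can contain post-treatment information, a judgement about matching that rests on that table, and asthma and eosinophil (above 0.4 × 10⁹/L) counts that can include patients who qualify only on later records. How many patients are affected cannot be derived from the document.

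Bias in the device comparison is conditional on matching or adjusting for these variables. In the illustration, matching on ever-recorded diabetes takes a true risk ratio of 2.00 to between 1.55 and 1.88, and 1.50 to between 1.38 and 1.45. The bias is towards no difference on a harm outcome. These figures rest on assumed rates, equal prevalence at IPD, and new diabetes being found by the same codes and prescriptions as the co-morbidity. The unchanged null in particular needs the equal prevalence.

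**What to change.** Before data extraction:

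1. Define every co-morbidity as recorded on or before IPD. For diabetes, use the same cut-off as the at-risk set of the diabetes outcome.
2. Take FEV1 % predicted, FEV1/FVC, GOLD group, mMRC and eosinophils as the last value on or before IPD, within the 5-year look-back.
3. Derive the asthma and eosinophil sub-populations from these pre-index values.
4. Use post-IPD values only in a labelled sensitivity analysis, and never for matching.

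This changes the query, not the data source. The cost is more missing severity and eosinophil values. The extent is unknown, partly because inclusion guarantees only one year of prior practice data, so some patients will have a look-back shorter than 5 years. Report the percentage missing by device, so that the loss and any difference between arms can be seen.

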Study 1: Exploratory study - identifying the benefits of pMDI versus Diskus for delivering fluticasone/salmeterol combination therapy in patients with chronic obstructive pulmonary disease (COPD)

Version Date: 7 February 2014

Protocol

**Study 1: Exploratory study -
identifying the benefits of pMDI
versus Diskus for delivering
fluticasone/salmeterol combination
therapy in patients with chronic
obstructive pulmonary disease
(COPD)**

To characterise patients with COPD initiating with fluticasone/salmeterol combination therapy via pMDI and Diskus and to identify and compare the potential benefits of using either device in the delivery of fluticasone/salmeterol combination therapy

Contents

OBJECTIVES	3
BACKGROUND	3
DATASOURCE	4
STUDY DESIGN	4
STUDY OUTCOMES	7
STATISTICAL ANALYSIS.....	8
TIMELINE, DELIVERY AND COSTINGS	9
RESEARCH TEAM	9
REFERENCES.....	9

OBJECTIVES

The aims of this exploratory study are to characterise patients with chronic obstructive pulmonary diseaseⁱ (COPD) initiating with fluticasone/salmeterol combination therapy delivered via pressurised metered dose inhaler (pMDI; also known as Evohaler) or Diskus (also known as Accuhaler); and to identify and compare the potential benefits of using either device in the delivery of fluticasone/salmeterol combination therapy.

This will be carried out by:

- (1) Characterising patients with COPD on fluticasone/salmeterol combination therapy via pMDI and Diskus.
- (2) Identifying and comparing the potential benefits of using pMDI versus Diskus in the delivery of fluticasone/salmeterol combination therapy in terms of both efficacy and adverse events, in particular:
 - a. Number of COPD exacerbations
 - b. Development of pneumonia infections
 - c. Type II diabetes diagnosis
 - d. Therapeutic indexⁱⁱ
 - e. Number of severe COPD-related events, including:
 - i. Lower respiratory tract infections
 - ii. Oral thrush

These are more clearly defined under 'Dataset Variables' below.

BACKGROUND

Inhaled corticosteroid use by patients with obstructive lung disease is associated with increased risk of pneumonia [1], increased risk of developing type-II diabetes [2] and increased risk of oral thrush [3].

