^{viii}**COPD-related Hospitalisations:** consist of either a definite COPD Emergency Attendance or a definite COPD Hospital Admission; OR a generic hospitalisation read code which has been recorded on the same day as a **Lower Respiratory Consultation*** (see below - excluding where the only lower respiratory code recorded on that day was for a lung function test).

^{ix}**Evidence of a Respiratory Review** - consists of the following:

- Antibiotics prescribed with evidence of a respiratory review^{ix}.

(2) COPD related adverse events

Where adverse events include the number of incidences of:

- Oral thrush
- Lower respiratory tract infections
- Bronchitis
- Dysphonia / hoarseness
- Nasopharyngitis (common cold)
- Sinusitis
- Hypokalemia (low blood potassium)
- Muscle or joint pain

(3) Therapeutic index

Therapeutic index = highest dose not causing harm (side effect) / lowest dose that causes benefit (reduced number of severe COPD-related events).

For the highest dose not causing harm: the median dose at which no (any) adverse events occur

For the lowest dose that causes benefit (reduced number of severe COPD-related events): median dose at which patients show no increase in number of exacerbations in outcome

STATISTICAL ANALYSIS

Statistically significant results will be defined as $p < 0.05$ and trends as $0.05 \leq p < 0.10$

Summary statistics will be produced for all baseline and outcome variables, as a complete dataset and by device. For variables measured on the interval or ratio scale, these will include:

Sample size (n) & percentage non-missing

Mean & Variance / Standard Deviation

Range (Minimum / Maximum)

Median & Inter-quartile Range (25th and 75th percentiles)

For categorical variables, the summary statistics will include:

Sample size (n)

Range (if applicable)

Count and Percentage by category (distribution)

Treatment arms will be compared using t-test / Mann Whitney U-test (depending on distribution) for variables measured on the interval/ratio scale and using a chi square test for categorical variables.

a) Any **Lower Respiratory Consultation*** (see below) and

b) Any additional respiratory examinations, referrals, chest x-rays, or events.

* **Lower Respiratory Consultations** - consist of the following:

a) Lower Respiratory read codes (including Asthma, COPD and LRTI read codes);

b) Asthma/COPD review codes excl. any monitoring letter codes;

c) Lung function and/or asthma monitoring.

TIMELINE, DELIVERY AND COSTINGS

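### HbA1c change is scored regardless of intervening anti-diabetic escalation, and no directional measure sits beside it, so a null HbA1c contrast could be misread as no harm

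*Protocol*

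**What the plan says.** Under Study Design, Dataset Variables, the protocol lists four items for development or progression of diabetes:

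- new diabetes in the outcome year, among patients without it at or before the index prescription date;
- progression to insulin, meaning "no insulin prescription during 1 year baseline period AND any insulin prescriptions during 1 year outcome period", which is a variable of its own;
- glycaemic control, entered as "Diabetic control (defined as change in HbA1c value prior to starting" treatment, with the second value taken later than the index prescription date;
- treatment change, also entered separately: "Diabetic medication (defined as change in anti-type-II diabetic medication dosage OR medication type".

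The HbA1c definition sets no condition on anti-diabetic treatment started or increased between the two values. Follow-up leaves time for such changes: "The outcome period will be one year following the index date".

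Under Statistical Analysis, devices are compared one variable at a time: "Treatment arms will be compared using t-test / Mann Whitney U-test (depending on distribution) for variables measured on the interval/ratio scale", and chi-square for categorical variables. No analysis links HbA1c change to medication change.

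The diabetes item in the Objectives is "Type II diabetes diagnosis". HbA1c change is not named there, nor among the three numbered items under Study Outcomes (exacerbations, adverse events, therapeutic index).

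**The concern.** Escalation of anti-diabetic treatment is a response to the quantity being measured. If a device raises HbA1c, more of its patients cross the level at which treatment is intensified, and their later HbA1c is lower than it would otherwise have been. A patient who deteriorated and was then treated can be scored as having improved control. This acts more often in the harmed group, so the contrast shrinks. It also widens the spread of changes in both groups.

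The neighbouring variables help only in part. The medication variable has no direction: a dose reduction, a switch and an added drug all count as a change. The insulin variable has a direction but captures only one form of escalation.

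The Background section cites increased diabetes risk with inhaled corticosteroids, so readers will look here for a glycaemic signal. A non-significant HbA1c comparison, reported as its own line, could be taken as reassurance about the worse device.

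**Working it through.** **Inputs.** The protocol gives no sample size, HbA1c SD, device effect or escalation rate, so there is no figure to reproduce. Every input below is an assumption. HbA1c is in percentage points and tests are two-sided at 0.05 (the protocol states 0.05 but not sidedness).

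**Step 1: the bias in closed form.** Let d be the device difference without drug changes, pA − pB the excess escalation on the worse device, and e the HbA1c fall per escalation.

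observed difference = d − (pA − pB) × e

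With d = 0.30:

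| Excess escalation | e = 0.5 | e = 1.0 |
|---|---|---|
| 0 points | 0.30 | 0.30 |
| 10 points | 0.25 (17% masked) | 0.20 (33%) |
| 20 points | 0.20 (33%) | 0.10 (67%) |
| 30 points | 0.15 (50%) | 0.00 (100%) |

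With equal escalation on both devices nothing is masked.

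**Step 2: how much excess the harm itself would generate.** Simulation assumptions: baseline HbA1c 7.2 (SD 1.0), within-patient SD 0.35, a mid-year reading, escalation in 30–90% of those above 7.5, a fall of 0.7–1.3 per escalation, and the whole harm of 0.30 present by mid-year. In the middle case (50%, fall 1.0), escalation is about 25% against 19%:

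0.30 − (0.25 − 0.19) × 1.0 = 0.24, so about a fifth is masked.

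These rates imply about 0.25/0.5 = 50% and 0.19/0.5 = 38% above the threshold. At the extremes:

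- 90%, fall 1.3: 0.30 − 0.9 × 0.12 × 1.3 = 0.16
- 30%, fall 0.7: 0.30 − 0.3 × 0.12 × 0.7 = 0.27 (0.28 simulated)
- 70%, fall 1.3: mean changes are −0.16 and −0.35, so both groups appear to improve and the difference is 0.19.

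If only half the harm is present at mid-year there is less masking, with up to 0.29 observed. The overall range is 0.16 to 0.29. The 20- and 30-point rows in Step 1 lie beyond what a harm of 0.30 produces here.

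**Step 3: precision.** Without escalation the SD of change is 0.35 × √2 = 0.49. In the middle case it is about 0.66. With an assumed 60 diabetic patients per device, √(2/60) = 0.183 and z = difference / (SD × 0.183):

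| Measure | Difference | SD | z | Power |
|---|---|---|---|---|
| Any value | 0.24 | 0.66 | 1.99 | about 51% |
| Last value before escalation | 0.30 | 0.49 | 3.35 | about 92% |
| Bias alone, SD unchanged | 0.24 | 0.49 | 2.68 | about 77% |

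So most of the apparent power loss comes from the wider SD, not from the bias. The high power in the second row also depends on the small SD. With an SD of change of 1.2, z is 1.37 for 0.30 (about 28% power) and 1.10 for 0.24 (about 19%).

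**Step 4: would escalation show up by itself?** For 25% against 19%, SE = √[(0.25 × 0.75 + 0.19 × 0.81)/n]. At n = 60 this is 0.075, z = 0.80 and power is about 12%. At n = 350 it is 0.031, z = 1.92 and power is a little under one half. If escalation were instead 15% against 25%, power at 350 would be about 91%. Whether the separate variable reveals the harm therefore depends on the assumed gap. These figures also treat it as directional, which as written it is not.

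**Step 5: does a pre-escalation value restore the contrast?** Only if the harm appears early. With half of it present at mid-year, the middle case gives about 0.267 for the pre-escalation value and 0.272 for any value. The attenuation is about the same, though the pre-escalation SD is smaller. With added random drift in HbA1c over the year, simulated power for the pre-escalation value is about 36–52% at 60 per device.

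**The case against.** The strongest reply is that the protocol does record the drug changes. Medication change and progression to insulin stand under the same heading as HbA1c and are summarised by device, so a null HbA1c result would be printed beside them. A reader might infer that the plan ignores anti-diabetic treatment; the text does not support that. What remains is narrower: the records are not connected to HbA1c, and the medication variable cannot separate escalation from reduction.

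Second, HbA1c regardless of treatment changes is a legitimate quantity, and how to handle intervening drugs is a choice of estimand that an SAP may settle. This stands against replacing the definition. It does not remove the point, because the protocol itself fixes the HbA1c and medication definitions.

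Third, the size rests wholly on assumptions, and the pre-escalation value has its own bias. It shortens exposure for escalated patients, selects high readings (the unharmed group shows a spurious rise of about 0.02 in the middle case) and loses patients escalated before any outcome-year HbA1c. This stands too. A reader might infer from the 92% in Step 3 that the pre-escalation value recovers the full signal; Step 5 shows that it need not.

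Fourth, it might be said that escalation need not differ by device. If escalation responds to HbA1c, a device that raises HbA1c produces that difference, so it follows from the harm being looked for.

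**Conclusion.** The point holds in a limited form. As defined, the HbA1c contrast is biased towards no difference, and is noisier, if one device raises HbA1c and so prompts more escalation before the later reading. The separate medication and insulin variables reduce this weakness but do not remove it. Under the stated assumptions a true 0.30 appears as 0.16 to 0.29, about 0.24 in the middle case. None of these figures can be derived from the protocol, and with equal escalation there is no bias.

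The reach is small. One exploratory variable is affected. A reader might extend the problem to the Objectives' diabetes item; that item concerns diagnosis and is served by the new-onset measure, which this mechanism does not touch. Nor does the point reach the three numbered outcomes. The practical risk is a null HbA1c result being quoted alone as reassurance. Adding measures is justified; replacing the existing one is not.

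**What to change.** Keep the any-value HbA1c change as it stands. Beside it, report by device:

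- **(a)** the proportion with worsened control, defined as an HbA1c rise above a pre-set amount or escalation of anti-diabetic treatment (added drug, dose increase or insulin start; reductions not counted);
- **(b)** HbA1c change using the last outcome-year value dated before first escalation, with the number of patients who have no such value.

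Add a sentence that a null any-value HbA1c difference is not to be read alone as absence of harm.

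The cost is protocol wording, a date comparison on prescribing and HbA1c records that the study already needs, and a little more analysis. Patients escalated before any outcome-year HbA1c contribute only to (a). Measure (b) can itself understate a harm that builds over the year. Measure (a) should not be expected to add much power: with a 0.5-point threshold it had about 57% at the assumed 60 per device. Its value is that it has a direction and keeps patients whom (b) loses.
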